5.1 Statistical Methods

5.1.1 Hypotheses and Statistical Methods for Primary Objective

5.1.1.1 Hypotheses

The rVE of QIV-HD to QIV-SD in terms of prevention of cardiovascular and/or respiratory hospitalization will be estimated for the primary endpoint as follows:

$$rVE = \left(1 - \frac{C_{QIV-HD}/N_{QIV-HD}}{C_{QIV-SD}/N_{QIV-SD}} \right) \times 100\%$$

where:

- C_{QIV-HD} and C_{QIV-SD} are the numbers of cardiovascular and respiratory hospitalization cases (first occurrence) meeting the considered primary endpoint definition in the QIV-HD and QIV-SD groups, respectively
- N_{QIV-HD} and N_{QIV-SD} are the numbers of subjects in the QIV-HD and QIV-SD groups, respectively

The following hypotheses will be tested:

$$H_0: rVE \leq 0\%$$

$$H_1: rVE > 0\%$$

5.1.1.2 Statistical Methods

Primary endpoint will be derived using database extracted from the Finnish national registers.

In case of more than one occurrence for the same subject, only the first occurrence will be considered in the estimation of rVE.

The two-sided 95% CIs for rVE will be calculated by an exact method assuming a binomial distribution of the number of cases in QIV-HD group conditional on the total number of cases in both groups:

Let $q = \frac{C_{QIV-HD}}{C_{QIV-HD} + C_{QIV-SD}}$, the proportion of cases belonging to QIV-HD group among the total number of cases. Given the total number of cases, C_{QIV-HD} has a binomial distribution ($q, C_{QIV-HD} + C_{QIV-SD}$). Thus, a CI for q may be constructed using the exact Clopper-Pearson method for binomial proportions.

As $\frac{q}{1-q} = \frac{C_{QIV-HD}}{C_{QIV-SD}}$, the rVE estimate given above may be restated as follows:

$rVE = \left(1 - \frac{c_{QIV-HD}/N_{QIV-HD}}{c_{QIV-SD}/N_{QIV-SD}} \right) \times 100\% = \left(1 - \frac{N_{QIV-SD}}{N_{QIV-HD}} \times \frac{q}{1-q} \right) \times 100\%$, which is a strictly decreasing function of q.

Finally, for the primary endpoint, a CI of the rVE may be constructed based on the CI of q.

For the primary endpoint, the superiority of the QIV-HD effectiveness over QIV-SD will be considered demonstrated if the lower bound of the two-sided 95% CI for the rVE is above 0%.

5.1.2 Hypotheses and Statistical Methods for Secondary and Observational Objectives

5.1.2.1 Hypotheses

No hypotheses will be tested.

5.1.2.2 Statistical Methods

The estimated rVE with 2-sided 95% CI will be computed in the same way as the primary objective. No hypotheses will be tested, but depending on the number of the first occurrence observed, the lower bound of the 2-sided 95% CI may be used for results interpretation.

The rVE with 95% CI will be computed only if at least 5 occurrences in total of the both groups and at least 1 for QIV-SD group are present.

Several analyses will be displayed per factor such as season, delay since vaccination, site localization, age (in class or continuous variable), sex, or specific comorbidities. An analysis will be also done excluding cases potentially linked to a COVID-19 occurrence.

In addition, a complementary analysis available in the appendix 15 of the Clinical Study Report (CSR) will be conducted based on person-year as denominator.

KM curves will be also produced for some endpoints. The occurrences are based on first occurrence corresponding to the endpoint analyzed. The data collection period will vary depending on the injection date, and censored in case of first occurrence of the endpoint or date of death or voluntary withdrawal (expected to be rare). See also 4.3.3.3.

The safety endpoints, per subject, will be summarized per vaccine group, with 95% CI for the main endpoints. CIs will be calculated using Clopper-Pearson method.

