Observational Endpoints:	
The following endpoints will be described for all subjects:
 

1) Clinical relative effectiveness of QIV-HD as compared to QIV-SD (between <math>\geq</math> 14 days after vaccination and up to 31 August of the year following the vaccination) for the first occurrence of the following endpoints:

• Unscheduled cardiovascular or respiratory inpatient hospitalization (primary discharge)

• Inpatient hospitalizations with primary discharge codes for diseases of the circulatory system and diseases of the respiratory system based on the diseases and the ICD-10 codes listed in the primary endpoints (for each code separately)

• Inpatient hospitalization with primary discharge diagnosis, death, inpatient hospitalization with primary and secondary discharge or admission diagnoses, hospital emergency room visits, and primary care visits to physician based on the ICD-10 codes listed in the secondary endpoints

• Death, all-cause

2) Long-term complications and need of care in terms of diagnosis of hip fracture, based on ICD-10 code S72 and disabilities based on the care allowance for pensioners/disability in the Social Insurance Institution register (KELA)

3) The following health care resources for all subjects

• Medications such as anti-influenza and antibacterial outpatient medications

• All unscheduled hospitalizations and hospital emergency room visits

• All acute primary care visits to a physician

4) Clinical relative effectiveness of QIV-HD as compared to QIV-SD against laboratory-confirmed influenza based on routine swabbing and laboratory-confirmed invasive bacterial diseases

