## 9.2 Secondary Endpoints and Assessment Methods

### 9.2.1 Effectiveness

The secondary endpoints for the evaluation of rVE are:

- 1) First occurrence between  $\geq 14$  days after vaccination and up to 31 May of the year following the vaccination of each of the following endpoints:

- Inpatient hospitalization with primary discharge diagnosis (using ICD-10 codes) for:
  - Diseases of the respiratory system, based on codes J00-J06, J09-J18, J20-J22, J40-J47, J80, J81, J85, and J86
  - Diseases of the circulatory system, based on codes I11, I16, I20-I25, I26, I27, I30, I31, I33, I38-I42, I46-I50, I63-I67, and I74-I76
  - Pneumonia, based on codes J12-J18
  - Heart failure, based on code I50
  - Acute myocardial infarction, based on code I21
  - Atrial Fibrillation, based on code I48
  - Stroke, based on code I63
  - Influenza and pneumonia, based on codes J09-J11 and J12-J18
  - Influenza, based on codes J09-J11
- Death, all-cause and based on the diseases and ICD-10 codes listed above
- Inpatient hospitalization with primary and secondary admission and discharge diagnoses based on the diseases and ICD-10 codes listed above
- Hospital emergency room visits based on the diseases and ICD-10 codes listed above
- Acute primary care visits to physician based on the diseases and ICD-10 codes listed above (or corresponding International Classification of Primary Care 2nd edition [ICPC-2] codes)

2) First occurrence between  $\geq$  14 days after vaccination and up to 31 May of the year following the vaccination of MACE as defined by all of the following endpoints:

- Ischemic heart diseases based on codes I20-I25
- Non-fatal myocardial infarction based on codes I21-I23
- Fatal or non-fatal stroke based on code I63
- Unstable angina based on codes I20 and I25

3) The following characterization for selected outcomes to be described when applicable:

- All occurrences of an unscheduled cardiovascular or respiratory inpatient hospitalization or hospital emergency room visits or primary care visits to physician
  - Onset of event
  - Duration of event

4) First occurrence between  $\geq$  14 days after vaccination and up to 31 May of the year following the vaccination of each of the endpoints listed above by:

- Age groups (65-74 years and  $\geq$  75 years or 65-79 years and  $\geq$  80 years)
- Groups with specific comorbidities (diabetes, cardiovascular history, chronic lung disease)

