## 9.3 Observational Endpoints and Assessment Methods

The observational endpoints for the evaluation of rVE are:

- 1) Clinical relative effectiveness of QIV-HD as compared to QIV-SD (between  $\geq$  14 days after vaccination and up to 31 August of the year following the vaccination) for the first occurrence of the following endpoints:
  - Unscheduled cardiovascular or respiratory inpatient hospitalization (primary discharge)
  - Inpatient hospitalizations with primary discharge codes for diseases of the circulatory system and diseases of the respiratory system based on the diseases and the ICD-10 codes listed in the primary endpoints (for each code separately)
  - Inpatient hospitalization with primary discharge diagnosis, death, inpatient hospitalization with primary and secondary discharge or admission diagnoses, hospital emergency room visits, and primary care visits to physician based on the ICD-10 codes listed in the secondary endpoints
  - Death, all-cause
- 2) Long-term complications and need of care in terms of diagnosis of hip fracture, based on ICD-10 code S72 and disabilities based on the care allowance for pensioners/disability in the Social Insurance Institution register (KELA)

- 3) The following health care resources for all subjects
  - Medications such as anti-influenza and antibacterial outpatient medications
  - All unscheduled hospitalizations and hospital emergency room visits
  - All acute primary care visits to a physician
- 4) Clinical relative effectiveness of QIV-HD as compared to QIV-SD against laboratory-confirmed influenza based on routine swabbing and laboratory-confirmed invasive bacterial diseases

Details of the assessment methods will be described in the statistical analysis plan (SAP).

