2.3 Observational Objectives

To evaluate the QIV-HD as compared to QIV-SD in terms of:

- 1) Clinical relative effectiveness over an extended period of time
- 2) Follow-up of functionality / dependence during the 3 periods of follow-up (ie, between ≥ 14 days after vaccination and up to 31 May and 31 August of each year and during the influenza peak period)
- 3) Health Care Utilization during the 3 periods of follow-up described above
- 4) Laboratory-confirmed influenza and invasive bacterial diseases as captured in the database based on routine practice between ≥ 14 days after vaccination and up to 31 May of the year following the vaccination and during the influenza epidemic period as defined by the Finnish epidemic thresholds

The endpoints for the observational objectives are presented in Section 9.3 of the protocol.

3 Description of the Overall Trial Design and Plan

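### Health care utilisation is compared only through each subject's first contact; a rate ratio of all stays and visits, shown beside it, would fit the objective better.

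*SAP*

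**What the plan says.** SAP 2.3 sets the third comparison of QIV-HD with QIV-SD as "Health Care Utilization during the 3 periods of follow-up described above". Protocol 9.3 item 3 lists the resources as outpatient medications, "All unscheduled hospitalizations and hospital emergency room visits" and "All acute primary care visits to a physician". Item 1 of the same list is limited to the first occurrence; item 3 is not. Protocol 9.3 leaves the assessment methods to the SAP.

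The SAP has one comparative rule for secondary and observational objectives (5.1.2.2): "The estimated rVE with 2-sided 95% CI will be computed in the same way as the primary objective". In the primary analysis (5.1.1.2), "In case of more than one occurrence for the same subject, only the first occurrence will be considered in the estimation of rVE".

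Three other outputs come close:
- Table 5.1 shows the number of occurrences next to the rVE.
- A complementary analysis "will be conducted based on person-year as denominator". SAP 4.3.3.3 ends rVE follow-up on the date of the first case.
- Kaplan-Meier curves are drawn for some endpoints, again on first occurrences.

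SAP 4.3 adds no method. For the observational endpoints it cites protocol Section 3, which covers study organization; the endpoints are in 9.3.

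**The concern.** Utilisation is naturally a volume: how many stays and visits each group generated. A first-occurrence analysis reduces each subject's count to any versus none, so one visit and ten visits weigh the same. For rare events this hardly matters. For common contacts, such as acute primary care visits for any cause, many subjects have at least one visit under either vaccine. A fall in total visits then shows only partly in the any-use proportion.

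No test is planned, but SAP 5.1.2.2 allows the lower confidence limit to be used in interpreting results. What the estimate measures, and how precisely, therefore bears on what the report will say about utilisation.

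**Working it through.** **The plan's own figure.** With X ~ Bin(2200, q), q = (1 − rVE)/(2 − rVE), and success when the Clopper-Pearson upper limit for q is below 0.5, power for rVE of 10 to 15% is 68.7, 77.3, 84.5, 90.0, 94.0 and 96.6%. This matches SAP Table 5.2. With about 450 cases (SAP 5.5) and rVE 13% it is 29%. The documents give no such figure for utilisation.

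**Inputs.** From SAP 3.1: 33,093 vaccinated, so n ≈ 16,546 per group at 1:1. Assumed, because the documents do not give them: negative binomial visits with mean m and dispersion k, and a rate ratio RR acting in proportion on all visits.

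**Formulas** (log scale):
- Share with any visit: p = 1 − (1 + km)^(−1/k), with m·RR in place of m for QIV-HD.
- First occurrence, ordinary risk ratio: variance = [(1 − p0)/p0 + (1 − p1)/p1]/n.
- First occurrence, SAP conditional interval: width from [1/p0 + 1/p1]/n, while the estimate still varies as in the line above.
- All-event rate ratio: variance = [(1/m + k) + (1/(m·RR) + k)]/n.
- With true log effect d, sampling SE s and interval SE c, the chance that the 95% interval excludes zero is Φ((d − 1.96c)/s) + Φ((−d − 1.96c)/s).

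**Worked case: m = 1, k = 1, RR = 0.95.**
- p0 = 0.500 and p1 = 0.95/1.95 = 0.487, so the first-occurrence rVE is 1 − 0.487/0.500 = 2.56%. Half of all visits are repeats.
- Ordinary risk ratio: d = 0.0260, s = √(2.053/16,546) = 0.0111, z = 2.33, giving Φ(0.37) = 65%.
- SAP interval: c = √(4.053/16,546) = 0.0157, giving Φ((0.0260 − 0.0307)/0.0111) = 34%.
- All visits: d = 0.0513, s = √(4.053/16,546) = 0.0157, z = 3.28, giving Φ(1.32) = 91%.

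A simulation of 2,000 trials gave 34.6% (SAP interval), 66.6% (ordinary) and 91.3% (all visits).

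| m | k | Cut in visits | First-occurrence rVE | SAP interval | Ordinary risk ratio | All-event rate ratio |
|---|---|---|---|---|---|---|
| 1 | 1 | 5% | 2.56% | 34% | 65% | 91% |
| 1 | 1 | 3% | 1.52% | 8% | 28% | 50% |
| 1 | 1 | 1% | 0.50% | 1% | 7% | 10% |
| 2 | 1 | 5% | 1.72% | 12% | 60% | 97% |
| 1 | 5 | 5% | 1.98% | 12% | 22% | 48% |
| 0.5 | 1 | 5% | 3.39% | 42% | 59% | 76% |
| 0.1 | 1 | 5% | 4.57% | 23% | 26% | 28% |

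For m from 0.6 to 2.5, k from 0.5 to 2 and cuts of 3 to 5%, the rate ratio gains 11 to 49 points over the ordinary first-occurrence interval. At m = 0.015 (the primary endpoint's share is 450/33,093 = 1.4%) all three methods give 8 to 9%.

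**Where the gap comes from.** In the worked case the full gap is 91 − 34 = 57 points. Of these, 65 − 34 = 31 come from the conditional interval being too wide when many subjects have an event. Only 91 − 65 = 26 come from dropping repeat visits.

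**A different effect pattern.** Let each subject's visit rate be exponential with mean 1 (the same m = 1, k = 1), and let the vaccine remove the same absolute amount δ from every rate, down to zero.
- A 5% cut in the mean needs e^(−δ) = 0.95. The any-use share becomes 0.95 × 0.5 = 0.475, so the first-occurrence rVE is 5%, with no dilution.
- First occurrence, ordinary interval: z = 0.0513/√(2.105/16,546) = 4.55, or 99.5%.
- All visits: the QIV-HD mean is 0.95 and the variance 0.95 + 0.9975 = 1.9475, so z = 0.0513/√((2 + 1.9475/0.9025)/16,546) = 3.24, or 90%.

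Here the order reverses.

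**The case against.** **The endpoint may not be a count.** Where the protocol means repeat events it can say so: secondary endpoint 3 in 9.2.1 reads "All occurrences of an unscheduled cardiovascular or respiratory inpatient hospitalization or hospital emergency room visits or primary care visits to physician". In item 3, 'all' may mean all-cause, as opposed to the listed ICD-10 codes. That stands, so the text shows an ambiguity and not a proven contradiction. An all-cause reading would still not imply first events only, and the SAP settles neither question.

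**These endpoints are descriptive.** The Synopsis says "The following endpoints will be described for all subjects", and SAP 5.1.2.1 tests no hypothesis. This also stands: the loss is one of estimand fit and precision, not of a powered test. The same Synopsis wording also covers items 1 and 4, which are explicitly about relative effectiveness, so it does not rule out an estimate with an interval.

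**Repeat use is reported.** A reader might infer that the plan ignores repeat visits altogether. It does not: Table 5.1 tabulates occurrences, and secondary endpoint 3 describes all cardiovascular and respiratory ones. Only the comparative estimate and its interval are missing.

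**The size is assumed.** Visit rates, dispersion and effect are not in the documents. The only stated effect, 13%, is for cardiovascular and respiratory hospitalization, and SAP 5.7 describes a season without significant influenza circulation. An effect near 1% leaves almost no gain.

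**Conclusion.** The point holds as a gap in how a descriptive objective is estimated. The SAP's only between-group estimate for utilisation uses first occurrences, and its person-year version does not add repeats, because follow-up stops at the first case. For common contacts under a proportional effect, the estimate is diluted (2.6% for a true 5%) and the chance of an interval excluding zero is 65% against 91%. Both figures rest on the assumed mean 1 and dispersion 1.

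Two stronger readings are tempting. One is to quote 34% against 91% as the cost of dropping repeats; more than half of that difference belongs to the interval method. The other is that the plan loses power in general. The documents claim no power for utilisation, the gain is small for rare events or effects near 1%, and it can vanish or reverse under another effect pattern. The primary endpoint is defined as a first occurrence and is not touched. The mismatch between any use and volume of use does not depend on the effect pattern, if the endpoint is meant as a volume. The change is a cheap improvement, not a correction on which the trial's conclusions depend.

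**What to change.** State in the SAP whether 'all' in protocol 9.3 item 3 means all-cause, all repeat events, or both. Then add to SAP 5.1.2.2:

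- For observational objective 3 (unscheduled hospitalizations, emergency room visits and acute primary care visits from Thl_hilm, Thl_er and Thl_avoh), estimate the QIV-HD/QIV-SD rate ratio of all occurrences per person-year, from vaccination plus 14 days to 31 May 2020 and to 31 August 2020.
- Person-time runs to period end, death or withdrawal and is not censored at the first event. This needs its own definition, because SAP 4.3.3.3 censors at the case.
- The 95% CI uses a subject-level robust variance, or a negative binomial model with log person-time offset.
- Show it as a descriptive estimate beside the first-occurrence rVE.
- Leave out the aggregated KELA panels, which have no subject-level counts, and the epidemic period, which SAP Section 4 says was not defined for 2019-2020.

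The cost is one paragraph and a few tables from panels already listed in the SAP, with no new data. Specify it before unblinding; otherwise label it post hoc. Frequent attenders weigh more in a count, which is one reason to keep the first-occurrence rVE alongside. AVOHILMO does not cover private outpatient clinics (protocol Table 11.1), so the primary care count describes public care only.

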#### 9.2.2.3.2 Serious Adverse Events

Information on non-fatal SAEs will be collected from the health registers, from inclusion until 6 months after vaccination. Non-fatal SAEs will not be individually assessed for causality. Instead, they will be evaluated statistically by comparing the frequency of SAEs to a baseline incidence estimated from the same health registers.

Information on SARs (suspected to be related to the vaccine by the HCPs), fatal SAEs, and AESIs will be collected and assessed throughout the study. Every SAR must be reported, even if the Principal Investigator considers that it is not related to the vaccine.

Any SAR (suspected to be related to the vaccine by the HCPs), fatal SAE, or AESI occurring at any time during the study will be reported by the Principal Investigator using the SAE electronic case report form (SAE eCRF) in the electronic data capture (EDC) system according to the Completion Instructions provided by the Sponsor. All information concerning the SAE is to be reported either as part of the initial reporting or during follow-up reporting if relevant information became available later (eg, outcome, medical history, results of investigations, copy of hospitalization reports. See [Section 10](#) for further details on SAE reporting).

For each SAR/AESI, the following information is to be recorded:

- Diagnostic (SAR/AESI) or ICD-10 code (Fatal: non SAR/AESI)
- Start and stop dates
- Whether the SAE was related to the investigational product

The Principal Investigator will assess the causal relationship between the SARs (suspected to be related to the vaccine by the HCPs), fatal SAEs, and AESIs and the investigational product as either “Not related” or “Related”, as described in [Section 9.2.2.3.3](#).

- Action taken for each SAE (eg, medication)

The action(s) taken by the subject to treat and/or manage any SAEs will be classified in the SAE eCRF using the following list (all applicable items should be checked):

- None
- Medication
- Health care provider contact
- Hospitalized

For each SAR/AESI, the Principal Investigator or a delegate will complete all the following criteria: outcome, elapsed time, and relationship to study procedures.

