[name]  
[name]

When the EDC system becomes available, the Principal Investigator must transcribe the information from the paper forms into the SAE eCRF in the EDC system.

To comply with current regulations on SAE reporting to health authorities, the Principal Investigator must document SARs (suspected to be related to the vaccine by the HCPs), fatal SAEs, and AESIs regardless of causal relationship, and notify the Sponsor and the CRA within the notification timelines stated in the following sections. The Principal Investigator will provide the Sponsor and the CRA with all necessary information to allow the Sponsor to conduct a detailed analysis of the safety of the investigational product. It is the responsibility of the Principal Investigator to request all necessary documentation (eg, medical records, discharge summary, in order to provide comprehensive safety information). All relevant information must then be transcribed onto the SAE eCRF.

Once the Sponsor confirms the reported event as SUSAR, the case will be managed according to SUSAR case management process (unblinding done by GPV; provide SUSAR case with unblinding information to the IDMC for further recommendation on relatedness of the case).

THL will report all non-fatal SAEs (except cardiovascular and respiratory hospitalizations [primary endpoints]) twice per month in the form of an aggregate table of SAEs with an evaluation based on background information and providing observed versus expected analysis of reported non-fatal SAEs.

The Sponsor will perform aggregate analysis of the non-fatal SAEs during safety management meeting every month for the first few months and every 3 months subsequently (depending on the need) during the study periods and at the end for final evaluation. For the blinded follow-up period, signal detection processes will be set up by comparing the frequency of safety outcomes to a baseline incidence estimated from the registers. This allows the safety assessment to be objectively based on probabilistic and statistical methods. The tabulated outputs will be generated by THL, under the Sanofi Pasteur GPV process.

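### The SAP plans no direct between-arm estimate for hospitalization SAEs by diagnosis outside the effectiveness codes, or for days 0–13, and does not say where the observed-versus-expected evaluation is reported

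*SAP*

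**What the plan says.** On how non-fatal SAEs are judged, protocol 9.2.2.3.2 says: "Non-fatal SAEs will not be individually assessed for causality". It continues: "Instead, they will be evaluated statistically by comparing the frequency of SAEs to a baseline incidence estimated from the same health registers". SARs suspected by a health care professional, AESIs and fatal SAEs keep an individual causality assessment (protocol 9.2.2.3.3).

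Protocol 10.1 says who does the comparison. THL sends a twice-monthly aggregate table "with an evaluation based on background information and providing observed versus expected analysis of reported non-fatal SAEs". The sponsor runs aggregate analyses "during the study periods and at the end for final evaluation". On method it says: "For the blinded follow-up period, signal detection processes will be set up by comparing the frequency of safety outcomes to a baseline incidence". On ownership: "The tabulated outputs will be generated by THL, under the Sanofi Pasteur GPV process". Protocol 11.1 adds that aggregated data on people outside the study may be collected as the baseline.

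On the final analysis, SAP 5.1.2.2 repeats protocol 12.1.2.2: "The safety endpoints, per subject, will be summarized per vaccine group, with 95% CI for the main endpoints", using Clopper-Pearson intervals. SAP Table 5.1 lists numbers and percentages of subjects with 95% CIs, and numbers of events. None of the 12 data panels in SAP section 4 is described as holding baseline incidence. SAP 4.3.1.1 counts each diagnosis code reported in a hospitalization as an SAE, and SAP 4.3.1.2 sets onset classes that begin with 0 to 13 days. SAP 5.7 records other safety changes (fatal and non-fatal hospitalizations analyzed together, seriousness taken from eSAEs only) but does not mention the baseline comparison.

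**The concern.** For register-identified non-fatal SAEs, a statistical evaluation stands in for case-by-case review. A reader would expect the SAP either to contain that evaluation or to point to it. It does neither.

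The one method that protocol 10.1 describes in any detail is tied to blinded follow-up. While the blind holds, the two arms cannot be separated, so an excess confined to one vaccine is diluted by the other arm.

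The trial has a better contrast available. The two arms share the same registers, season and recruitment, and their comparison needs no external baseline. Without a direct estimate, the study report will show two columns of percentages and leave the comparison to the reader, including for the first two weeks after vaccination, which no effectiveness endpoint covers.

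**Working it through.** **1. Which events have what.** The plan's provisions, set side by side:

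| Event | Individual causality review | Between-arm estimate planned |
|---|---|---|
| Suspected SARs, AESIs | Yes (protocol 9.2.2.3.3) | None; per-arm summary |
| Deaths | Yes (protocol 9.2.2.3.3) | rVE for all-cause death from day 14 (protocol 9.2.1, SAP 5.1.2.2) |
| Circulatory and respiratory hospitalizations in the effectiveness codes | Only if judged an endpoint-related SAR (protocol 10.6) | rVE from day 14 |
| All unscheduled hospitalizations, any diagnosis | No | Observational endpoint (protocol 9.3); the rVE method of SAP 5.1.2.2 may apply, in follow-up periods starting at day 14 |
| Other hospitalization SAEs, by diagnosis | No | None |
| Hospitalization SAEs, days 0–13 | No | None |

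The last two rows are the gap.

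**2. Why pooling matters.** Suppose an event rate doubles in QIV-HD only, arms are equal, and the baseline equals the QIV-SD rate. The pooled observed/expected ratio is (2 + 1)/2 = 1.5. The between-arm ratio is 2.

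**3. What a between-arm estimate would deliver.** The plan states no precision or power figure for safety; its power table concerns the primary endpoint only, so there is nothing to reproduce here.

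Inputs: 33 093 vaccinated (SAP 3.1) and 1:1 allocation (SAP 5.5), so n = 33 093/2 ≈ 16 546 per arm. The documents give no SAE rate, so the rates p below are assumptions.

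- Expected cases per arm: x = n × p.
- 95% CI for a risk ratio (RR) whose true value is 1: exp(±1.96 × √[2(1/x − 1/n)]).
- Half-width for the risk difference: 1.96 × √[2p(1 − p)/n].
- Detectable RR: two-proportion calculation, two-sided 0.05, 80% power.

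Worked line for p = 1%: x = 165.5; √[2(1/165.5 − 1/16 546)] = 0.109; 1.96 × 0.109 = 0.214; exp(±0.214) = 0.81 to 1.24.

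| Assumed rate per arm | Cases per arm | RR 95% CI | Risk-difference half-width (percentage points) | Detectable RR |
|---|---|---|---|---|
| 10% | 1654.7 | 0.94–1.07 | 0.65 | 1.09 |
| 1% | 165.5 | 0.81–1.24 | 0.21 | 1.33 |
| 0.1% | 16.5 | 0.51–1.98 | 0.07 | 2.24 |
| 0.01% | 1.7 | 0.12–8.63 | 0.02 | 7.26 |

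These are normal approximations. They are rough in the last row, and the reported intervals should be exact or score intervals.

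**4. The 0–13 day class.** Days 0 to 13 are 14 of roughly 182 days in six months, or 0.077. At a constant rate, a category at 1% over six months would be at about 0.08% in this class, just below the 0.1% row. A category at 10% would be at about 0.8%, close to the 1% row.

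**5. Number of intervals.** One overall plus six dated onset classes gives 7 per diagnosis category. Ten categories give 70 intervals, of which up to about 70 × 0.05 = 3.5 would exclude no difference by chance alone.

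**The case against.** The strongest reply is that nothing has been omitted. Protocol 10.1 places the observed-versus-expected work in pharmacovigilance, with an evaluation at the end of the study, while the SAP covers the analyses for the study report. A missing baseline panel is what one would then expect. This stands: a reader might infer that the baseline comparison is never made, and the documents do not support that. What remains is that the SAP gives no pointer to it, and that no arm-specific method is described for the final evaluation.

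Second, no between-arm safety test was promised. The safety objective is to describe, no secondary hypotheses are tested, and protocol and SAP use the same sentence. This also stands, so the absence is not a breach. An estimate with an interval is nonetheless compatible with a descriptive objective.

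Third, much is already covered: time to onset, duration, eSAE seriousness and outcome are tabulated; deaths and the effectiveness codes have rVE from day 14; and the IDMC sees unblinded safety data (protocol section 3). This narrows the gap to the last two rows of the table above. The IDMC review does not put an estimate in the study report.

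Fourth, a reader can compute a risk ratio from the reported counts. True, but prespecifying it settles the analysis set, the method and the categories before unblinding.

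**Conclusion.** The point holds as a cheap improvement. The final analysis lacks a direct between-arm estimate for hospitalization SAEs by diagnosis outside the effectiveness codes and for days 0–13, and the SAP does not say where the observed-versus-expected evaluation is reported or whether it changed.

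The gain is real for categories at about 1% or more (RR interval about 0.81–1.24 or narrower) and small for rare events (0.51–1.98 at 0.1%). These figures rest on equal arms and assumed SAE rates.

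Two further inferences are tempting and should not be drawn. One is that safety will be judged by whether the two arms' separate intervals overlap, and so at a very strict level: neither document states such a rule. The other is that a healthy-participant effect would hide a vaccine-specific excess in the baseline comparison: the documents give neither the participants' risk relative to the baseline nor a definition of the baseline population, so no size can be put on it.

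**What to change.** 1. In SAP 5.1.2.2, add the QIV-HD versus QIV-SD risk ratio or risk difference with an exact or score 95% CI for hospitalization SAEs by ICD-10 chapter or block, overall and for the existing onset classes, including 0 to 13 days.
2. State the analysis set. SAP 5.2 uses the injected group for almost all outputs; if this contrast does too, say so, or give the randomized group.
3. Label the intervals as unadjusted signal screening that is weak for rare events.
4. In SAP 5.1.2.2 or 5.7, state where the observed-versus-expected evaluation is reported, or record it as changed.
5. Do not present the between-arm contrast as the evaluation named in protocol 9.2.2.3.2. That section names a comparison with a register baseline.

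The cost is extra columns in tables already planned and one or two sentences. No new data are needed. The drawback is a large set of unadjusted intervals, some of which will exclude no difference by chance.
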